10.12.2 Safety Analyses

The Safety population will be used for the analysis of safety assessments.

For continuous variables data will be summarised by treatment using n, mean, SD, minimum and maximum values. For categorical variables data will be summarised by treatment using frequency and percentage.

10.12.2.1 Adverse Events

Adverse events will be coded using the latest version of MedDRA.

Separate summaries of serious adverse events, and adverse events resulting in discontinuation of study treatment will be presented.

11 Adverse Events (Definitions and Reporting)

The Investigator or duly trained designee(s) will be responsible for detecting, documenting and reporting AEs and SAEs during this study as detailed in this section of the protocol.

11.1 Adverse Events

An adverse event (AE) is defined as any unfavourable or unintended sign, symptom, or disease that occurs or is reported by the participant to have occurred, or a worsening of a pre-existing condition. An AE may or may not be related to the study treatment.

AEs will be elicited through direct questioning and participant reports. Any abnormality in physical examination findings or laboratory results that the Investigator believes is clinically significant to the research participant will be reported as an AE. Abnormal findings that are NOT clinically significant should not be recorded as an AE.

11.2 Reporting and Follow-up of Adverse Events

Report initiation for all AEs and serious adverse events (SAEs), (see Section 11.4) will begin at the time of the first run in phase visit and will be reported up until the final study visit. All events will be followed to resolution or until 30 days after the participant completes the study, whichever comes first. A final assessment of outcome will be made at that time.

AEs that emerge prior to the randomisation visit (TV1), will be recorded on an AE form. Aside from being used to determine participant eligibility, this information will permit the Investigator to record the nature, duration and severity of any ongoing baseline medical conditions prior to the patient receiving study treatment.

All AEs must be recorded in the participant's medical records and on the CRF. AEs will be reported using customary medical terminology along with the following information: the onset and end dates, whether the event is at the site of the study ulcer or at the site of the investigational device, whether the event is related to the study treatment, whether the event is related to the study ulcer, whether the event is considered to be an SAE (see Section 11.3), the impact the event had on study treatment (see Section 11.2.1), the Common Terminology Criteria for AEs (CTCAE) grade (intensity) of the event (see Section 11.2.2), the relatedness of the event (see Section 11.2.3), whether treatment was given as a result of the event (see Section 11.2.4), and the outcome of the event (see Section 11.2.5).

11.2.1 Impact on Study Treatment

The impact the event had on the study treatment will be assessed as either: none, study treatment interrupted, study treatment discontinued, or not applicable. The "not applicable" assessment will be used only when the participant is no longer in the treatment phase of the protocol.

11.2.2 Intensity Assessment

The guidelines outlined in CTCAE v4.03 will be used for assessing the intensity of the event. The general guidelines for assessing the AE grade appear below. Full guidelines may be obtained at <http://evs.nci.nih.gov/ftp1/CTCAE>.

Table 3: Common Terminology Criteria for AEs v4.03 General Guidelines

Grade	Description
Grade 1	Mild; asymptomatic or mild symptoms; clinical or diagnostic observations only; intervention not indicated.
Grade 2	Moderate; minimal, local or noninvasive intervention indicated; limiting age-appropriate instrumental activities of daily living (ADL)*.
Grade 3	Severe or medically significant but not immediately life-threatening; hospitalisation or prolongation of hospitalisation indicated; disabling; limiting self care ADL†.
Grade 4	Life-threatening consequences; urgent intervention indicated.
Grade 5	Death related to AE.‡
* Instrumental ADL refer to preparing meals, shopping for groceries or clothes, using telephone managing money etc	
† Self care ADL refer to bathing, dressing and undressing, feeding self, using toilet, taking medications, and not bed ridden.	
‡ Unlike the AE outcome assessment, a participant may have more than one Grade 5 event	

11.2.3 Relatedness Assessment

Adverse events will be assigned a relationship (relatedness) to the study treatment. The Investigator will be responsible for determining the relationship between an AE and the study treatment. The type of event, organ system affected, and timing of onset of the event will be factors in assessing the likelihood that an AE is related to the study treatment. Relatedness of AEs to study treatment will be classified as follows:

- Not Related: No relationship exists between the AE and the treatment. The event is attributed to a pre-existing medical condition or an intercurrent event unrelated to the study product.
- Possibly Related: Follows the treatment, but may have developed as a result of an underlying clinical condition or treatments/interventions unrelated to the study product.
- Probably Related: Follows the treatment, but is unlikely to have developed as a result of the participant's underlying clinical condition or other treatment or other interventions.
- Definitely Related: Follows the treatment and physical evidence shows a convincing relationship to the treatment.

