2.2 Safety assessment

Safety will be assessed based on incidence of adverse events (AEs), incidence of serious AEs (SAEs), incidence of study treatment related AEs, incidence of investigational device related AEs, ulcer infection, and incidence of pain in the ulcer site (sudden onset of pain or increase in pain during the study treatment).

3 Study Design

This study is designed as a prospective, multicentre, randomised, assessor blinded study designed to compare the efficacy including participant reported outcomes of two different gekoTM treatment durations in conjunction with SC, with each other and with SC alone, in the treatment of patients with venous leg ulcers. There will therefore be two arms in the study consisting of: 1) participants randomised to receiving SC only; 2) participants randomised to receiving SC, and gekoTM 12 hours daily.

The standard care therapy in this study is multilayer, multicomponent compression therapy intended for the treatment of VLU. A non-adherent (NA) wound contact dressing and/or an absorbent dressing may be used if required, at the Investigator's discretion in addition to SC. All dressing use and reason for dressing use will be recorded.

Multiple multilayer, multicomponent compression bandaging systems delivering levels of compression and with clinical data to support their use are commercially available. The compression bandaging system of choice based on local best practice will be used. Moreover, this will prevent any problems around consistency of method of application of compression.

The study will be a multinational, multicentre study with study centres in the UK and Europe

The study will have three phases: a four-week Run-in Phase, a four-week Treatment Phase and a twelve-week follow-up phase. A schematic picture of the study flow is provided below in Figure 1.

[figure not shown]

Figure 1: Study Schedule

At or up to 21 days before the first Run-in Phase Visit (RV1), the Investigator or suitably qualified designee will, prior to the performance of any protocol-specific procedure, obtain written informed consent from the patient.

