10.7.4 Safety Assessments

Safety will be assessed using the following parameters:

- Incidence of AEs

- Incidence of SAEs
- Incidence of study ulcer infection
- Incidence of study treatment related AEs (including geko™, compression bandaging and any dressings used to treat the study wound)
- Incidence of investigational device (geko™) related AEs
- Pain in the ulcer site (sudden onset of pain or increase in pain during the study Treatment Phase)

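### One relatedness grade per adverse event, against an inconsistently named treatment, has to serve two separate safety endpoints, so geko-related events cannot be separated reliably or completely

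*Combined protocol and SAP*

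**What the plan says.** **Endpoints.** Section 10.7.4 lists "Incidence of study treatment related AEs (including geko™, compression bandaging and any dressings used to treat the study wound" and, as a separate parameter, "Incidence of investigational device (geko™) related AEs". Section 2.2 makes the same split: "incidence of study treatment related AEs, incidence of investigational device related AEs". The synopsis repeats both.

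**Causality grade.** Section 11.2.3 has the investigator grade each event once: "Adverse events will be assigned a relationship (relatedness) to the study treatment". The four levels are introduced by "Relatedness of AEs to study treatment will be classified as follows". The definition of the lowest level uses another term: "The event is attributed to a pre-existing medical condition or an intercurrent event unrelated to the study product". The next level, Possibly Related, also refers to the study product. The synopsis gives geko as the study product and multilayer compression as the comparator product.

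**Other items per event.** Section 11.2 also records "whether the event is at the site of the study ulcer or at the site of the investigational device", and whether the event is related to the study ulcer. It lists no item for relatedness to the device.

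**Impact on treatment.** Section 11.2.1 has one field, with the options "none, study treatment interrupted, study treatment discontinued, or not applicable". Section 10.12.2.1 plans a summary of events that led to discontinuation of study treatment.

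**Analysis.** Sections 10.12.2 and 10.12.2.1 describe no relatedness summary and do not say which of the four grades count as related. Section 10.12 leaves detailed methods to a later SAP.

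**The concern.** Participants in the geko arm also receive compression, and dressings where needed, so attribution is the main device-safety question. Section 1.5 reports skin irritation in earlier geko case studies and ascribes it to the condition of the patients' skin. Section 1.6 names eczema at the application site as the device risk, and expects wound pain, infection and maceration in any participant because of the ulcer itself. Ulcer-site pain is a safety parameter in its own right, and could come from the device, the bandage, a dressing or the ulcer.

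If the investigator gives one grade against an undivided treatment, background reactions to standard care enter the device profile. If sites differ on what the grade refers to, the pooled incidence mixes two quantities. A later SAP cannot repair either problem, because the judgement it would need was never collected.

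**Working it through.** No sample size, power or event count is involved, so there is nothing to recompute. The check sets the required outputs beside the items collected.

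| Output required (2.2, 10.7.4) | Judgement needed | Item in 11.2 to 11.2.5 |
|---|---|---|
| Events related to study treatment (geko, compression, dressings) | Causality against the bundle | One four-level grade, term inconsistent |
| Events related to geko | Causality against geko alone | None; only device-site location |

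1. **Read the scale as the bundle.** This follows the lead sentence of 11.2.3 and the definition in 10.7.4. The composite endpoint is then covered. In the geko arm, an event graded as related could be due to geko, compression or a dressing, and the grade does not say which. The geko endpoint has no causality item.

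2. **Read the scale as geko.** This follows the study product wording in 11.2.3 and the synopsis. The geko endpoint is then covered. The composite endpoint has no item, and a standard-care participant has no geko to be graded against.

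3. **Either way, one grade serves two endpoints.** The text supports both readings, so sites may differ.

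4. **Add the location item.** Counting events that are both graded related and at the device site gives a usable approximation for local reactions such as application-site eczema. It misses any device effect elsewhere on the leg. It records where an event is, not what caused it, and the plan does not name it as the derivation.

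5. **Add the study-ulcer item.** Relatedness to the ulcer helps to set aside events due to the underlying disease. It does not divide the remainder between geko and standard care.

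6. **Cut-off.** Even with two grades, the incidence is undefined until the plan says whether Possibly Related counts.

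7. **Impact field.** The single field in 11.2.1 does not show which component was interrupted or stopped. This affects only the discontinuation summary in 10.12.2.1, and has no bearing on deriving geko-related events.

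**The case against.** The strongest reply is that the protocol already holds most of what is needed. Section 11.2.3 uses the study product term, and its Probably Related level contrasts the treatment with other treatments or interventions, so the scale can fairly be read as a geko scale. The device risks the protocol anticipates are local, and device-site location is recorded. The randomised standard-care arm receives compression and dressings without geko, and safety data are summarised by treatment, so an excess of related events in the geko arm would show at group level. The CRF may carry a device item, and a SAP is still to come.

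Much of this stands, and it rules out three stronger readings:

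- A reader might infer that geko-related events cannot be derived at all. The documents do not support that: the location item gives a proxy for the anticipated local reactions, and on the geko reading of the scale it is the composite endpoint that lacks a grade.
- A reader might infer that a device stop can never be told from a compression stop. That is wrong beyond the 11.2.1 field. The Appendix 6 diary records daily geko use and non-use. Section 9.8 records bandage removal and its reason. Section 9.9.7 has compression changes during infection entered in the CRF, and section 5.2 has reasons for treatment discontinuation recorded.
- A reader might try to size the problem by assuming rates of device and compression reactions. The documents give no rates for this, and such a figure would ignore the concurrent control arm.

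The reply does not supply the missing judgement. A group-level contrast is not event-level causality, which is what an incidence of device-related events calls for. Ambiguous wording lets sites grade differently, and a SAP written later cannot create a grade that was not collected.

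**Conclusion.** The point holds in a limited form. The plan requires two relatedness incidences and specifies one relatedness grade, against a treatment that it names in two ways. As written, geko-related events cannot be separated reliably or completely from compression- or dressing-related events. On the alternative reading, the composite endpoint and the standard-care arm have no applicable grade.

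No numerical size can be given from the documents. The gap is greatest for events away from the application site, where location offers no help, and smaller for local skin reactions. It affects a stated safety endpoint and leaves the primary efficacy result untouched, so it should be corrected but does not threaten the trial's main conclusion. The impact-field gap is minor, because other records hold component-level information.

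This assumes that the CRF follows the item list in section 11.2. The CRF was not available. If it already has a device-relatedness item, what remains is to state that in the protocol, settle the terminology and define the cut-off.

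**What to change.** In sections 11.2 and 11.2.3:

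- Grade relatedness separately to geko (not applicable in the standard-care arm) and to compression/dressings, each on the existing four-level scale. The composite endpoint then follows: an event is study-treatment-related if either grade meets the cut-off.
- Choose one defined term for what is being graded and use it throughout, including in the category definitions.
- State which grades count as related, and carry that into the safety analysis text and the SAP.

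As a minor addition, have the 11.2.1 item name the component affected (geko or standard care). The 10.12.2.1 discontinuation summary could then be split without linking to the diary and bandage records.

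**Cost.** One or two extra CRF items per event, a short protocol and SAP edit, and a one-off query for events already recorded. That query has a real drawback: it asks for attribution after the fact from investigators who know the allocation, since section 10.4 blinds only the wound expert. Grades obtained that way should be flagged as retrospective.

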11.2.4 Treatment Given as a Result of the Event

The event impact in terms of treatment provided will be as either: none, medication administered, therapy administered, surgery, or other (with a specification).

11.2.5 Outcome Assessment

The outcome of the event will be assessed as either: resolved, resolved with sequelae, ongoing, or death. Only one AE per participant is allowed to have an outcome assessment as “death.” If there are multiple causes of death for a given participant, only the primary cause of death will have an outcome of death.

11.3 Serious Adverse Events

A SAE is defined as any AE that:

- Results in death
- Is life threatening (the participant is at immediate risk of dying from the adverse experience)
- Requires participant hospitalisation or prolongs existing hospitalisation
- Results in persistent or significant disability/incapacity
- Is a congenital anomaly/birth defect

11.4 Reporting of Serious Adverse Events

Once the Investigator becomes aware of an SAE, he/she must report the SAE to Sponsor within 24 hours.

Sponsor's SAE Contact:

[name] , PhD

[contact]

e-mail [contact]

A written SAE report must include a full description of the event. Additional supporting documentation may be requested and should be provided to Sponsor as and when it becomes available. Such documentation includes but is not limited to lab reports, electrocardiogram [ECG] reports, discharge summary, hospital notes, etc.

The Investigator is also responsible for reporting all SAEs to the appropriate Institutional Review Board (IRB) or in accordance with local laws and regulations. The Investigator is responsible for maintaining documentation in the study file that indicates the IRB has been properly notified.

11.5 SAE Follow-up

All events will be followed to resolution or until 30 days after the participant completes the study. A final assessment of outcome will be made at that time.

12 Direct Access to Source Data/Documentation

Participants will be identified on CRFs by a unique participant identification number and on source documents by name and date of birth. No personal identifier will be used in any publication or communication used to support this research study. The participant identification number will be used if it becomes necessary to identify data specific to a single participant.

The monitors, auditors, personnel authorised by the Sponsor, the local IRB, and regulatory agencies are eligible to review medical and research records related to this study as a part of their responsibility to protect human participants in clinical research and will be given direct access to source data and documentation (e.g., medical charts/records, printouts etc.) for source data verification, provided that participant confidentiality is maintained in accordance with local requirements. Access to electronic medical records may be governed by institution policy and each site will be required to ensure access while remaining compliant with institutional requirements.

13 Quality Control and Quality Assurance

13.1 Monitoring Requirements

In order to maintain knowledge of the progress of a study, the Sponsor's designated Clinical Research Associate (CRA)/monitor will visit the centres during the study as well as maintain frequent telephone and written communication. The Investigator will permit the Sponsor to monitor the study as frequently as is deemed necessary and provide access to medical records to ensure that data are being recorded adequately, that data are verifiable and that protocol adherence is satisfactory.

The Investigator will permit representatives of the Sponsor and/or designated CRO to inspect all CRFs and corresponding study participant original medical records (source documents) at regular intervals throughout the study. Participant original medical records and other relevant data must be available to support all data recorded in the CRF. In addition to the original medical records, these data may include but is not limited to, study, laboratory and diagnostic reports, wound images and tracings, quality of life questionnaire, etc.

Site inspections serve to verify strict adherence to the protocol and the accuracy of the data being entered on the CRFs, in accordance with applicable regulations. A Monitoring Log will be maintained at each study site which the monitor will sign, date and state the type of visit.

The Investigator should be aware that the study site and participant records might be inspected and audited by the Sponsor or representatives of Sponsor or relevant regulatory authorities.

13.2 Acceptability of Case Report Forms

A CRF must be completed for each participant who has signed an informed consent form. For patients who are screen failures, this would be limited to the screen failure CRF page. All source documents and CRFs will be completed during or as soon as possible after the participant's visit. The Investigator will review CRFs to indicate that, to his/her knowledge, they are complete and accurate. CRFs will be reviewed by the Sponsor's CRA/ monitor, who will make a decision as to their acceptability.

13.3 Modification of Protocol

A modification or alteration to this protocol may not be undertaken without first obtaining the concurrence of Sponsor. Both the Lead Investigator and the Sponsor representative must sign and date the amendment prior to implementation. In addition, the Lead Investigator must report all protocol amendments to, and receive all required approvals from, the Institutional Review Board/Independent Ethics Committee (IRB/IEC) PRIOR to implementation of any protocol amendment at the study centre, with two exceptions:

1. When necessary to eliminate apparent immediate hazard to the participant; or
2. When the modification involves only logistics or administration.

In the event that a protocol change is proposed for all participants, the following procedure for a protocol amendment will be followed. An amendment must be in writing and it must be dated

by both the Sponsor and the Investigator. If necessary, the Sponsor will submit protocol amendments to the appropriate regulatory authorities and notify other Investigators using this protocol.

An amendment may also require modification of the informed consent form. The Investigator will provide an approval letter for the amendment and revised informed consent form, if applicable, to the Sponsor.

Any protocol amendments will be listed in the "Appendices" portion of the Table of Contents.

13.4 Reporting Protocol Deviations

The Investigator is obligated to follow the protocol without departure from the requirements written in the protocol. If the Investigator deviates from the protocol requirements, the Sponsor will make the determination as to whether the participant will continue in the study. The Sponsor also has the right to discontinue the participant for protocol deviations/violations.

All protocol deviations must be documented in the CRFs.

14 Ethics and Regulatory Requirements

This study is to be conducted in accordance with the specifications of this protocol and in accordance with principles consistent with Declaration of Helsinki, Good Clinical Practice (GCP) and currently applicable regulations.

No protocol changes will be implemented without the prior review and approval of the relevant IRB/IEC s, except where it may be necessary to eliminate an immediate hazard to a research participant (See Section 14.1).

Additionally, all study products used in this study are manufactured, handled and stored in accordance with applicable Good Manufacturing Practices (GMP) and the products provided for this study will be used only in accordance with this protocol.

